2.2 Background

Congenital ichthyosis is a large, heterogeneous family of inherited skin disorders of cornification resulting from an abnormality of skin keratinization (1).

The management of CI is a life-long endeavor, which remains largely symptomatic (ie, emollients with or without keratolytics) and commonly focused on reducing scaling and/or skin lubrication with both systemic and topical treatments (1). A first-line therapy includes hydration and lubrication accomplished by creams and ointments containing low concentrations of salt, urea, or glycerol, which increases the water-binding capacity of the horny layer. Addition of keratolytics is used to decrease corneocyte cohesiveness, to promote desquamation, and to dissolve keratins and lipids (eg, α -hydroxy acids, salicylic acid, high-dose urea, propylene glycol, *N*-acetylcysteine, and retinoids). Systemic retinoid treatment is reserved for those patients who are refractory to topical agents because of long-term adverse effects and teratogenicity (5); however, the investigational use of oral isotretinoin has demonstrated remarkable efficacy when used for the treatment of ichthyoses and is believed to be attributable to isotretinoin's ability to reduce comedogenesis by decreasing hyperkeratinization (1, 5). For the treatment of CI, it would be desirable to have a topical formulation of isotretinoin as it would afford targeted delivery of the

drug at the disease tissue site, while potentially minimizing systemic exposure compared to that of systemic retinoid treatment, and additionally providing hydration and lubrication to the diseased skin.

2.3 Benefit/Risk Assessment

While no topical isotretinoin formulation is approved for use in treatment of CI (or any indication in the US), topical formulations of isotretinoin (eg, 0.05% gel and 0.1% cream) have demonstrated some efficacy in reducing the clinical signs associated with ichthyosis and other disorders of keratinization. In one study, topical 13-cis-RA (isotretinoin) cream 0.1% demonstrated a marked reduction in scaling and an improvement in skin smoothness after 4 weeks of treatment in 40% of subjects (2/7 patients with non-erythrodermic LI, 2/2 patients with Darier's disease, and 0/1 patients with autosomal dominant ichthyosis vulgaris). However, this clinical improvement was accompanied by local skin irritation (eg, itchy erythema) in responders, and dose modifications were often prescribed to mitigate such effects (12). Similarly, topical isotretinoin gel, 0.05% (Isotrex®) demonstrated partial resolution or clearance of hyperkeratosis and papules in the treatment area (10 cm² area) after 3 months of treatment (up to twice daily [bid] as tolerated) in 50% (6/12) of patients with Darier's disease.

In addition, systemic retinoids, including isotretinoin, have been used for the investigational treatment of CI and have demonstrated remarkable efficacy in reducing the clinical signs of the disease while dosing of the drug is maintained (1, 5).

More recently, a pilot Phase 2a, multicenter study in subjects ≥ 12 years of age showed topically applied TMB-001 ointment (0.1%) to be safe, tolerable, and supporting a favorable efficacy signal with improvement in overall IGA for CI treatment.

As with any retinoid, the side effects of TMB-001 may include the following local skin reactions (LSRs): burning, dryness, edema, erythema, hyperpigmentation, hypopigmentation, photosensitivity, pruritus, scaling/peeling, stinging, and tenderness.

Although systemic exposure is expected to be low given the route of topical administration. In minipigs receiving once daily dermal applications of TMB 001 ointment at concentrations of 0% (control), 0.025%, 0.1%, and 0.2%, there was little to no systemic absorption of isotretinoin with most values being near or below the limit of quantitation (0.374 ng/mL).

In addition, in a Phase 2a clinical study of subjects with CI, the concentrations of isotretinoin and tretinoin were measured. Plasma concentrations of isotretinoin and tretinoin indicated that systemic exposure was minimal within the 4 hours following initial application. Trough concentrations measured on Days 8, 29, 57 and 84 approximately 12 hours following the preceding dose indicated that systemic concentrations of isotretinoin and tretinoin were within range of the endogenous levels measured at Baseline prior to the first application.

The most notable adverse reactions with oral isotretinoin are: dry lip, dry skin, back pain, dry eye, arthralgia, epistaxis, headache, nasopharyngitis, chapped lips, dermatitis, renal or hepatotoxicity, musculoskeletal discomfort, teratogenicity, and visual acuity reduced.

The following are concerns for women of childbearing potential (WOCBP):

- Severe birth defects can occur during pregnancy while taking oral isotretinoin, with any amount and even if taken for short periods of time;
- Pregnancy must be avoided 1 month before, during, and for 1 month after treatment.

More detailed information about the known and expected benefits and risks and reasonably expected adverse events (AEs) of TMB-001 ointment may be found in the Investigator's Brochure.

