5.1 Inclusion Criteria

To enter the study, a subject must meet the following criteria:

1. Subject is male or female, 9 years of age and older at Visit 2 (Baseline).
2. Subject has provided written informed consent/assent. A subject under 18 years of age must provide written informed assent and be accompanied by the parent or legal guardian at the time of consent/assent signing. The parent or legal guardian must provide informed consent for the subject. If a subject becomes 18 years of age during the study, the subject must provide written informed consent at that time to continue study participation.
3. Females must be postmenopausal (defined as amenorrhea greater than 12 consecutive months in women 50 years of age and older), surgically sterile (hysterectomy, bilateral salpingectomy, or bilateral oophorectomy), or use acceptable forms of birth control. Women of childbearing potential (WOCBP) must have a negative urine pregnancy test (UPT) at Visit 2 (Baseline) (UPTs must have a minimum sensitivity to detect 25 mIU beta-human chorionic gonadotropin [β -hCG]/mL). Methods of acceptable contraception are further defined in [Appendix 6](#). Female subjects who become sexually active or begin to have relations with a partner during the study must agree to use 2 forms of birth control for 30 days prior to having relations and to continue such forms for the duration of the study.
4. Subject has clinical diagnosis of CI and has a genetic confirmation of either ARCI-LI (eg, transglutaminase 1-deficient) or RXLI (eg, deletion of steroid sulfatase gene) subtypes of CI. For ARCI-LI subjects, enrollment is not limited to Transglutaminase 1 mutations. Other genetically confirmed ARCI-LI mutations can potentially be enrolled as long as the phenotype is consistent with ARCI-LI and the other inclusion criteria are met, as determined by the Investigator. Congenital Ichthyosis XomeDxSlice will be used to diagnose both RXLI and ARCI-LI. GeneDx tests detect transglutaminase mutations in the TGM1 gene, X-linked recessive steroid sulfatase mutations in the STS gene, and additionally analyzes 47 other genes linked to CI. This is a multi-gene panel testing so that all known causes of CI can be confirmed/ruled-out since there is phenotypic overlap between the subtypes (including STS). The tests are considered Laboratory Developed Tests (LDTs) and are thus regulated per US regulations 42 CFR 493 and the laboratory is accredited by the College of American Pathologists.

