5.2 Exclusion Criteria

A subject is ineligible to enter the study if he/she meets 1 or more of the following criteria:

1. Subject is pregnant, lactating, or is planning to become pregnant during the study.
2. Subject has inflammatory skin diseases that confound the interpretation of results (eg, atopic dermatitis) unrelated to ichthyosis.
3. Subject has previously failed on topical/oral retinoid therapy for treatment of CI.
4. Subject, in the Treatment/Assessment Areas, has used: (a) topical retinoids or any other topical prescription or over-the-counter therapies (except emollients, keratolytics, and topical steroids - see below), that are intended for, or that in the opinion of the Investigator, may improve CI within 2 weeks of Visit 2 (Baseline), or (b) keratolytics or topical corticosteroids within 5 days prior to Visit 2 (Baseline).
5. Subject has used any topical products in the Treatment/Assessment Areas, including bland emollients, on Visit 2 (Baseline) prior to randomization.
6. Subject has used ultraviolet (UV) treatment within 4 weeks prior to Visit 2 (Baseline).
7. Subject has undergone systemic therapies using vitamin A supplements or St. John's Wort within 4 weeks prior to Visit 2 (Baseline). Note: Use of a multivitamin including Vitamin A is not exclusionary provided it is taken as directed on the packaging.
8. Subject has used systemic retinoids within 12 weeks of Visit 2 (Baseline) or any other systemic therapies that are intended for or may improve CI within 4 weeks of Visit 2 (Baseline).
9. Subject is immunosuppressed (eg, human immunodeficiency virus, systemic malignancy, graft host disease) or receives systemic immunotherapy.

10. Subject is currently taking concomitant immunosuppressive drugs, including systemic corticosteroids, within 2 weeks of Visit 2 (Baseline).
11. Subject has untreated secondary infections; however, subject may become eligible after successful treatment of his/her infection(s) at the Investigator's discretion.
12. Subject is currently enrolled in an investigational drug or device study or has used an investigational drug or investigational device treatment within 30 days prior to Visit 2 (Baseline).
13. Subject has lesions suspicious for skin cancer (skin cancer not ruled out by biopsy) or untreated skin cancers within the Treatment/Assessment Areas.

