8.1.1 Visit 1 (Screening)

Screening will occur at Visit 1 (Day -90 to Day -7). Subjects can be screened for the study up to approximately 90 days before Baseline. During Screening, the study requirements and procedures will be reviewed and written informed consent/assent will be obtained prior to the initiation of any study-related procedures. Following informed consent, a review of inclusion exclusion will be conducted so that the Investigator can assess if the subject is likely to be eligible for enrollment. Once this is confirmed, the availability of genetic testing confirming the diagnosis of CI and specific subtype will be addressed. Subjects who already have had genetic test documenting ARCI-LI or RXLI types of CI will not be required to provide samples for genetic testing. However, the subject must provide the Investigator with a copy of the genetic report for the source documentation file. Subjects requiring genetic testing, will have a buccal specimen obtained and sent for analysis. Following confirmation of the appropriate genetic subtype, the following procedures will be completed in the Screening period; Demographics, medical history, concomitant medications, physical exam, vital signs, clinical evaluation of extent and location of CI, percent BSA with CI in the Treatment Area, as well as in the VIIS Assessment Area, and

clinical laboratory test as found in [Table 7](#). In addition, VIIS for scaling will be performed for the VIIS Assessment Area and IGA for Scaling and Fissure will be performed for the Treatment Area.

Subjects who meet all inclusion criteria and no exclusion criteria will be randomized to a treatment group stratified by CI subtype. Randomization will be performed as specified in [Section 6.3](#).

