8.5 Treatment of Overdose

Overdose in this study can be defined as either oral ingestion of a tube of TMB-001 or applying the TMB-001 ointment more than the protocol specified regimen of twice daily.

Oral ingestion of a tube of TMB-001 ointment 0.1% would result in less exposure than achieved with the recommended dosage of oral isotretinoin. Consequently, the theoretical occurrence of symptoms of overdosage (eg, hypervitaminosis A) is highly unlikely.

If a subject does receive an overdose of TMB-001 ointment, the subject should be counseled about the teratogenicity of isotretinoin and counseled on the prevention of pregnancy. Any WOCBP must be evaluated for pregnancy and must be warned to avoid pregnancy per the contraceptive measures outlined in the protocol for at least 1 month after overdose. Men should use a condom or avoid reproductive sexual activity with a female who is or might become pregnant for at least 1 month after an overdose. Subjects who present with an overdose should not donate blood for at least 1 month.

In the event of an overdose, the Investigator should:

1. Contact the Medical Monitor immediately.
2. Closely monitor the subject for any AEs, SAEs, and laboratory abnormalities for 1 month after the overdose.
3. Obtain a plasma sample for pharmacokinetic analysis if requested by the Medical Monitor (determined on a case-by-case basis).
4. Document the quantity of the excess dose as well as the duration of the overdose in the eCRF.

Decisions regarding dose interruptions or modifications will be made by the Investigator in consultation with the Medical Monitor based on the clinical evaluation of the subject.

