Appendix 6 Contraceptive Guidance and Collection of Pregnancy Information

Definitions:

Woman of Childbearing Potential (WOCBP)

A woman is considered fertile following menarche and until becoming postmenopausal unless permanently sterile (see below).

Women in the following categories are not considered WOCBP:

1. Premenarchal
2. Premenopausal female with 1 of the following:
 - a) Documented hysterectomy.
 - b) Documented bilateral salpingectomy.
 - c) Documented bilateral oophorectomy.

Note: Documentation can come from the study center personnel's: review of the subject's medical records, medical examination, or medical history interview.
3. Postmenopausal female:
 - a) A postmenopausal state is defined as no menses for 12 months without an alternative medical cause. A high follicle stimulating hormone (FSH) level in the postmenopausal range may be used to confirm a postmenopausal state in women not using hormonal contraception or hormonal replacement therapy (HRT). However, in the absence of 12 months of amenorrhea, a single FSH measurement is insufficient.
 - b) Females on HRT and whose menopausal status is in doubt will be required to use 1 of the non-estrogen hormonal highly effective contraception methods if they wish to continue their HRT during the study. Otherwise, they must discontinue HRT to allow confirmation of postmenopausal status before study enrollment.

Contraception Guidance

Female subjects of childbearing potential are eligible to participate if they agree to use a highly effective method of contraception consistently and correctly as described in [Table 8](#) below.

Table 8 Highly Effective Contraceptive Methods

Highly Effective Contraceptive Methods That Are User Dependent^a Failure rate of < 1% per year when used consistently and correctly.

Combined (estrogen and progestogen containing) hormonal contraception associated with inhibition of ovulation^b
 
 • Oral. • Intravaginal. • Transdermal.

Progestogen only hormonal contraception associated with inhibition of ovulation
 
 • Oral. • Injectable.

Highly Effective Methods That Are User Independent^a

Implantable progestogen only hormonal contraception associated with inhibition of ovulation^b
 
 • Intrauterine device (IUD). • Intrauterine hormone-releasing system (IUS). 
Bilateral tubal occlusion.

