
Vasectomized partner A vasectomized partner is a highly effective birth control method provided that the partner is the sole male sexual partner of the WOCBP and the absence of sperm has been confirmed. If not, an additional highly effective method of contraception should be used.

Sexual abstinence Sexual abstinence is considered a highly effective method only if defined as refraining from heterosexual intercourse during the entire period of risk associated with the study treatment. The reliability of sexual abstinence needs to be evaluated in relation to the duration of the study and the preferred and usual lifestyle of the subject.

NOTES:

^a Typical use failure rates may differ from those when used consistently and correctly. Use should be consistent with local regulations regarding the use of contraceptive methods for subjects participating in clinical studies.

^b Hormonal contraception may be susceptible to interaction with the study treatment, which may reduce the efficacy of the contraceptive method. In this case, 2 highly effective methods of contraception should be utilized during the treatment period and for at least 30 days after the last dose of study treatment.

Pregnancy Testing:

- WOCBP will only be included in the study after a confirmed negative urine pregnancy test at Visit 2 (Baseline). The UPT must have a minimum sensitivity of 25 mIU beta human chorionic gonadotropin.
- Additional pregnancy testing will occur at times specified in the schedule of assessments during the treatment period, at the Visit 6 (EOS), and as required locally.

Collection of Pregnancy Information

Female subjects who become pregnant

- The Investigator will collect pregnancy information on any female subject who becomes pregnant while participating in this study. Information will be recorded on the appropriate form and submitted to the Sponsor within 24 hours of learning of a subject's pregnancy. The subject will be followed to determine the outcome of the pregnancy. The Investigator will collect follow-up information on the subject and the neonate, and the information will be forwarded to the Sponsor. Generally, follow-up will not be required for longer than 6 to 8 weeks beyond the estimated delivery date. Any termination of pregnancy will be reported, regardless of fetal status (presence or absence of anomalies) or indication for the procedure.

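### Section 2.3 requires pregnancy to be avoided from 1 month before to 1 month after treatment, but no eligibility or contraception clause covering all women of childbearing potential states that window

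*Protocol*

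**What the plan says.** Protocol Section 2.3, under concerns for WOCBP, states: "Pregnancy must be avoided 1 month before, during, and for 1 month after treatment".

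The clauses that sites apply read as follows.

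- **Inclusion 3 (Section 5.1), general duty.** Females who are not postmenopausal or surgically sterile must use acceptable birth control, and WOCBP need a negative urine pregnancy test at Baseline. No period is given.
- **Inclusion 3, special clause.** Females who become sexually active during the study must use two forms for 30 days before relations and "continue such forms for the duration of the study".
- **Exclusion 1 (Section 5.2).** "Subject is pregnant, lactating, or is planning to become pregnant during the study".
- **Appendix 6, Contraception Guidance.** WOCBP are eligible if they "agree to use a highly effective method of contraception consistently and correctly". No period is given.
- **Appendix 6, Table 8 note b.** Where hormonal contraception may interact with study treatment, "2 highly effective methods of contraception should be utilized during the treatment period and for at least 30 days after the last dose".
- **Appendix 6, Table 8, abstinence row.** Abstinence counts only if it means "refraining from heterosexual intercourse during the entire period of risk associated with the study treatment". The period of risk is not defined.
- **Section 8.5.** After an overdose, WOCBP "must be warned to avoid pregnancy per the contraceptive measures outlined in the protocol for at least 1 month after overdose".

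**The concern.** Section 2.3 sets a three-part window: a month before, the treatment period, and a month after. Sites enrol on Section 5 and counsel from Appendix 6, and neither states that window for WOCBP in general. A site applying those clauses exactly could enrol a woman who intends to conceive just after Visit 6, because Exclusion 1 does not reach her. It could also enrol a woman who began contraception only days before the first dose, because no clause sets a lead-in. Both cases run against Section 2.3.

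Follow-up does not close the gap either. The last scheduled pregnancy test is at Visit 6. Appendix 6 collects pregnancy information on subjects who become pregnant while participating, and investigators are not obliged to seek later pregnancy-related serious events. What is at stake is reproductive safety in a retinoid trial, and a protocol that sites can apply in one way. The efficacy results are not at stake.

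**Working it through.** The plan gives no figure to reproduce. The check sets each clause against the three parts of the Section 2.3 window and then works out the timing.

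**Clause by clause**

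| Clause | Applies to | Month before first dose | During treatment | Month after last dose |
|---|---|---|---|---|
| Inclusion 3, general | All WOCBP | Not stated | Implied | Not stated |
| Inclusion 3, special | Newly sexually active females | No: its 30 days run before relations, not before dosing | Yes | No, if the study ends for her at Visit 6 |
| Exclusion 1 | All females | No | Yes (intent to conceive) | No, on the same reading |
| Appendix 6 guidance | All WOCBP | Not stated | Implied | Not stated |
| Table 8 note b | Users of marked hormonal methods, where interaction is possible | No | Yes | Yes, at least 30 days |
| Table 8 abstinence row | Subjects relying on abstinence | Undefined | Yes | Undefined |
| Section 8.5 | Subjects with an overdose | No | Not applicable | 1 month after the overdose, by measures that carry no general duration |

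No row that applies to all WOCBP fills the first or last column. No row at all, general or conditional, expressly requires contraception for a month before the first dose.

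**Timing after treatment**

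Inputs: Visit 6 is Day 85 ± 7 (Section 8.1.4), a subject completes the study at Visit 6 (Section 4.4), and 1 month is assumed to be 30 days.

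- End of the post-treatment month, nominal: 85 + 30 = Day 115.
- Earliest Visit 6: 85 − 7 = 78, and 78 + 30 = Day 108.
- Latest Visit 6: 85 + 7 = 92, and 92 + 30 = Day 122.

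No visit or pregnancy test is scheduled after Visit 6. For a newly sexually active female treated to Visit 6, the special clause in Inclusion 3 covers 0 of these 30 days, if the study means her own participation. For other WOCBP the text is silent, apart from note b and the abstinence row.

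**Timing before treatment**

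Input: "Screening will occur at Visit 1 (Day -90 to Day -7" (Section 8.1.1), with the first dose on Day 1.

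- Latest Screening is about 7 days before the first dose.
- Lead-in days that can fall before Screening: 30 − 7 = 23 (22 if a Day 0 is counted).

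The visit schedule therefore does not supply a one-month lead-in by itself. A 30-day lead-in would fit, since up to 90 days are allowed.

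**The case against.** **It is an omission, not a contradiction.** No clause permits pregnancy inside the window. Section 2.3 is protocol text, and Appendix 2 requires conduct in accordance with the whole protocol. That is true as far as it goes. But subjects are admitted on the Section 5 criteria, and a mandatory rule found only in the introduction is easily missed.

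**The sentence may be carried over from the oral drug.** The list follows the adverse reactions of oral isotretinoin, and the bullet before it concerns the oral form. This reading is possible. However, the bullet itself refers to treatment without that limit, and the protocol applies similar periods to TMB-001: 30 days after the last dose in note b, and 1 month after an overdose, which includes applying the ointment more than twice daily. If the window is meant for the oral drug only, Section 2.3 is what needs correcting.

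**The 0-of-30 figure depends on a reading.** Section 4.4 also defines the end of the study as the last subject's last visit globally. On that reading, the clauses tied to the study would run past most subjects' own Visit 6 and could cover the post-treatment month for all but late finishers. This stands as a qualification. It makes the duration depend on other subjects' progress, and it does not help the general duties, which state no period.

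**The 23 days are not unprotected days.** A woman already using contraception is covered throughout, and genetic confirmation and laboratory work may lengthen screening. This is correct. The figure shows only what the schedule allows.

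**Partial coverage may be wider than described.** Note b opens with hormonal contraception in general, and in the extracted Table 8 the intrauterine devices sit under a heading marked b. The abstinence row could be read together with Section 2.3. Even so, coverage remains conditional on the method used.

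**Reach is limited.** The frequency of the X-linked subtype is given for males, so WOCBP would come mainly from the other subtype among about 45 subjects. Entry from age 9 means that some females may be premenarchal. Section 2.3 reports trough concentrations within the endogenous range. Pregnancy tests are done at Visits 2, 4, 5 and 6, and at Screening as needed (Table 7). All this bears on how serious the gap is, not on whether it exists.

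**Conclusion.** The point holds. Section 2.3 states a window that no general eligibility or contraception clause carries out. The lead-in month is not expressly required of anyone. The post-treatment month is stated only for some hormonal users and after an overdose.

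In size, there are about 30 days after Visit 6 with no scheduled visit and no general contraception duty, and up to about 23 lead-in days that can precede Screening. These figures assume a 30-day month, treatment to Visit 6, and the study ending for a subject at her own Visit 6.

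The number of WOCBP is not given, so the number of subjects affected cannot be stated. The consent text was not available and may state the window, but the protocol clauses would still lack it. No endpoint or analysis changes. The wording should be fixed because the rule concerns reproductive safety and correcting it costs little.

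**What to change.** 1. In Inclusion 3 and the Appendix 6 Contraception Guidance, require all WOCBP to use the specified contraception from at least 1 month before the first dose until at least 1 month after the last dose.
2. In the Inclusion 3 clause for newly sexually active females, replace the end point tied to the study with 1 month after the last dose.
3. Extend Exclusion 1 to pregnancy planned within 1 month after the last dose.
4. Define the period of risk in the abstinence row of Table 8 as the same window.
5. Align the consent text.

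If the sponsor judges the window unnecessary for topical use, it should instead revise Section 2.3 and give the rationale.

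The cost is wording in three places and matching consent text. A few WOCBP may need about 30 days of screening instead of as few as 7, still inside the 90 days allowed. There is no statistical cost.
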